## 8.0 PRETREATMENT EVALUATION

### Day – 6 weeks

Within 6 weeks of registration, patients will be seen by a hepatobiliary surgeon, GI oncologist, or interventional radiologist and, if general criteria for the study are met, he/she will have a triple phase CT. They will have vital signs (weight, blood pressure, temperature, heart rate) checked. After review of the CT, informed consent will be obtained by the interventional radiologist PI or Co-I, and the patient will be randomized. This will allow for stratification into patients whose treatment is expected to be complete after one embolization procedure, and those who will need two embolization procedures to complete their first treatment. Patients randomized to the LC

Bead (Bead + Dox) group will also have a cardiac echo or a MUGA scan to determine baseline ejection fraction (EF) if they have not had an evaluation of their EF within 3 months.

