### **What Constitutes a “Treatment”?**

A single “treatment” is defined as the administration of Bead Block, or LC Bead and Bead Block to the entire tumor burden evident on pre-procedure imaging. In the case of multifocal bi-lobar

disease this would, by definition, involve embolization of both right and left hepatic arteries. Solitary tumors may also be supplied by right and left hepatic arteries, particularly when they are large and arise in the anterior right liver, or in the medial segment of the left. Patients with HCC typically have underlying liver disease, and cirrhosis. As portal hypertension progresses, these patients become more reliant on hepatic arterial blood flow and hepatic failure following arterial embolization is a recognized risk of the procedure. For this reason, the entire hepatic arterial circulation is not embolized at once. Even patients without cirrhosis who are embolized for metastatic disease have a higher risk of hepatic failure when the entire liver is treated at one sitting [Brown KT, 1998, 1999]. Thus, a single session of embolization may not constitute a “treatment” as defined above.

For the purposes of this study when multifocal bilobar disease is present, a “treatment” is defined as treatment of both the right and left hepatic artery, and therefore will consist of two embolization sessions. This will be evident on the pre-procedure CT, and patients stratified accordingly. Patients with large solitary tumors may require embolization of more than one side of the liver as well. For example, patients with large tumors arising in segment IV may require embolization of the entire left hepatic artery as well as the anterior division of the right hepatic artery. Similarly, patients with large tumors in the anterior division of the right liver may require embolization of the entire right hepatic artery, plus segment IV. This is typically evident on the pre-procedure CT, and the need for 1 or 2 embolizations to complete treatment will be stratified for. If, in the operator’s judgment, it is not safe to perform any embolization in one session the treatment will be staged, even if this only becomes evident at the time of embolization. For the purposes of the study, two embolization sessions necessary to completely treat the initial tumor burden would constitute a single “treatment”.

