Patients with small tumors, or tumors localized to either the right or left liver, typically have the entire tumor burden treated in one session. Findings on the initial triple phase CT will typically identify which patients can be completely treated in one embolization session, and which patients will require a second session, thus randomization performed following the initial triple phase CT will be stratified to take this into account.

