## **14.0 BIOSTATISTICS**

This primary objective of this study is to estimate the response rates (CR + PR) to treatment following hepatic arterial embolization of hepatocellular cancer (HCC) using microscopic beads + Doxorubicin and beads alone by conventional RECIST criteria. With 50 patients in each arm response rates can be estimated to within +/- 14%. Patients will be randomly assigned to one the two treatment arms. A two-arm study was deemed necessary because there was not sufficient preliminary data on the control arm to design a single-arm study with historical controls. This is not a study where the goal is to test a hypothesis, rather the emphasis is on the estimation of response rates in the two arms. For this reason the sample size justification is provided in terms of the precision (half length of the asymptotic confidence interval) of these estimates instead of a power calculation. This is in the same spirit with most randomized Phase II trials of chemotherapeutic agents.

Randomization will be performed using the Clinical Research Database (CRDB), the central computing facility for clinical research at MSKCC. This system will generate a treatment assignment using the method of permuted blocks, at the time the patient is registered. Due to the nature of the treatment, the interventional radiologist will not be blinded but the radiologists assessing response to treatment will be blinded to treatment assignment.

One of the secondary objectives is to quantify the amount of necrosis in the two treatment arms and correlate this with conventional RECIST response as well as time to progression. With 50 patients in each arm, percent necrosis can be estimated to within +/- 14% of its standard deviation. Using 50% necrosis as threshold we plan to evaluate the degree of agreement between RECIST and necrosis response using Cohen's kappa and McNemar's test.

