Another secondary objective is to establish whether the use of the doxorubicin eluting beads might prolong time to progression (TTP), or survival, and if initial imaging response to treatment, as manifested by necrosis, correlates with either endpoint. This aim relates to analysis with censored outcomes (time-to-progression and survival time). We will use the Kaplan-Meier method to estimate the survival probabilities and we will use the log-rank test to compare groups. With 50 patients in each arm, we will have approximately 80% power to detect a hazard ratio of 3, assuming a median follow-up of 3 years (i.e., about half of the patients expiring) and controlling the Type I error rate at 5%. A hazard ratio of 3 corresponds to improving the median survival by three-fold or improving two-year survival by approximately 20%. We do not anticipate a survival difference of this magnitude so this aim will primarily serve to obtain preliminary data to plan a future definitive trial.

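### Randomisation is stratified by one versus two expected embolization sessions, but the planned log-rank test for TTP and survival ignores the stratum and Sections 14.0 and 15.2 never name it (minor)

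*Combined protocol and SAP*

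**What the plan says.** Stratification is stated four times, always outside the statistics and randomisation sections.

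- Section 8.0 (Day – 6 weeks), on randomising after CT review: "This will allow for stratification into patients whose treatment is expected to be complete after one embolization procedure", as against those who will need two procedures.
- Section 9.0, on what constitutes a treatment, for multifocal bilobar disease: "This will be evident on the pre-procedure CT, and patients stratified accordingly".
- The same subsection, for large solitary tumors: "the need for 1 or 2 embolizations to complete treatment will be stratified for".
- The end of that subsection: "randomization performed following the initial triple phase CT will be stratified to take this into account".

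Sections 14.0 and 15.2 both describe the allocation in the same words: "This system will generate a treatment assignment using the method of permuted blocks, at the time the patient is registered". Neither names a stratification factor.

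For TTP and survival, Section 14.0 plans Kaplan-Meier estimates and then "we will use the log-rank test to compare groups". It mentions no strata, covariates, Cox model or hazard ratio estimate. It also says of the trial as a whole: "This is not a study where the goal is to test a hypothesis".

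**The concern.** When allocation is balanced within strata, the analysis should normally use the same strata. If the stratum predicts outcome and the test ignores it, the test's variance does not reflect the balance the design has created. The test then rejects less often than its nominal level under the null and loses power under the alternative. It does not become anti-conservative.

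The protocol itself gives reason to think the factor may be prognostic. Two sessions mark multifocal bilobar disease or large tumors (Section 9.0), and tumor extent counts as an adverse indicator in the Okuda staging of Appendix 3.

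TTP has a further structural link. Section 4.1 times local progression from randomisation. The scan schedule in Section 10.0 runs from completion of treatment, and a second session follows the first by 2–6 weeks. Two-session patients will therefore tend to be scanned later on the TTP clock. Comparing arms within strata deals with this.

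Two practical matters follow.

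- Someone setting up the allocation from Section 15.2 alone would programme unstratified blocks.
- Section 9.0 lets a treatment be staged when the need is seen only during the procedure, so planned and actual sessions can differ. If the plan does not say which one defines the stratum, that choice could be made after randomisation.

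**Working it through.** **Inputs from the documents.** 100 patients, 50 per arm (Section 1.0). For survival, "about half of the patients expiring", so about 50 deaths; target hazard ratio (HR) 3; about 80% power; 5% type I error, sidedness not stated (Section 14.0). Two-sided is used here.

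**Assumptions (not in the documents).** Two-session share 30% or 50%. Stratum HR (two-session v one-session) 1, 1.5, 2 or 3. TTP events 70 or 90. Block size 4.

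**1. The plan's own figure.** Power = Φ(√D × ln HR / 2 − 1.960). With D = 50 and HR = 3: √50 = 7.071, ln 3 = 1.099, 7.071 × 1.099 / 2 = 3.884, and Φ(3.884 − 1.960) = 97.3%. The stated 80% is not reproduced. That is a separate matter and this point does not depend on it. It does mean that power at HR 3 is already near its ceiling, so any gain from stratifying looks small there.

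**2. HR detectable with 80% power.** HR = exp(2 × (1.960 + 0.842) / √D):

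- D = 50: exp(5.604 / 7.071) = 2.21
- D = 70: exp(5.604 / 8.367) = 1.95
- D = 90: exp(5.604 / 9.487) = 1.81

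**3. Simulation.** Permuted blocks within stratum, exponential times, no censoring before the analysis, analysis at the 50th, 70th or 90th event, and 20,000 trials per setting. The Monte Carlo standard error is about 0.3 points for power and 0.15 for type I error; for the paired differences at the detectable HR it is 0.08–0.26 points.

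Change in power from stratifying, in percentage points (30% / 50% two-session share):

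| Setting | Stratum HR 1 | 1.5 | 2 | 3 |
|---|---|---|---|---|
| Survival, 50 deaths, arm HR 2.21 | -0.2 / -0.3 | +0.4 / +0.6 | +1.9 / +2.2 | +5.7 / +6.3 |
| Survival, 50 deaths, arm HR 3 | 0.0 / +0.1 | 0.0 / +0.1 | +0.5 / +0.6 | +1.9 / +1.9 |
| TTP, 70 events assumed, arm HR 1.95 | -0.4 / -0.4 | +0.7 / +0.8 | +2.5 / +3.4 | +7.9 / +10.1 |
| TTP, 90 events assumed, arm HR 1.81 | -0.8 / -0.8 | +0.6 / +1.2 | +3.1 / +4.7 | +8.2 / +12.7 |

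The underlying power for the first row at 30% share, plain v stratified, is 78.8 v 78.6%, 78.2 v 78.6%, 76.8 v 78.7% and 72.6 v 78.3%. A separately coded simulation (6,000 trials per setting, arm HR 2.2) gives 72.3 v 78.7% at stratum HR 3 and 30% share.

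**4. Type I error.** The plain test is at about 5% for stratum HR 1 to 1.5, 4.1–4.7% at 2 and 3.0–3.8% at 3. The stratified test stays at 4.7–5.5%.

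**5. Effect estimate** (50 deaths, within-stratum HR 2.2, 5,000 trials per setting). The median unstratified Cox HR is 2.20–2.21, 2.16–2.18, 2.13–2.14 and 2.05 at stratum HR 1, 1.5, 2 and 3. The stratified median is 2.18–2.21. At stratum HR 3 the root-mean-square error of the log HR, measured against the within-stratum value, is 0.303–0.306 stratified and 0.284–0.288 plain. Stratifying removes the attenuation but does not improve precision.

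**6. Sensitivity to a misjudged stratum.** The CT will not always predict the number of sessions. If 15% of patients are assumed to be in the wrong stratum, the gain at stratum HR 3 falls from 6.1 to 2.5 points (50 deaths, arm HR 2.21, 30% share) and from 12.2 to 4.8 points (90 events, arm HR 1.81, 50% share). At stratum HR 2 with 50 deaths it hardly changes. These re-runs used 3,000 trials each, so their starting values differ slightly from the table.

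**The case against.** The strongest case is that this is a preference rather than an error. Section 14.0 does not say the test is unstratified; that is read from its silence. The factor is defined elsewhere in the same protocol, and permuted blocks are compatible with stratification, so the omission from 15.2 is editorial. The plain test is valid, the endpoints are secondary, and the plan describes this aim as a source of preliminary data for a later trial. At the protocol's HR of 3 the gain is nearly nil. The larger figures need a strong stratum effect and, for TTP, event counts the documents do not give. The simulation also ignores early removal from study and the scheduled nature of the scans.

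Most of this stands, and it is why the point is minor. The TTP figures in particular should be read as illustrative. It does not remove the point. If a stratified test was intended, the same sentence is still needed. If it was not, the design collects a balancing factor and then leaves it out of the comparison. The objection that a stratified Cox model does not improve precision is correct, and none is claimed. The reasons to report it are that it matches the stratified test, avoids attenuation when the stratum is prognostic, and gives a later trial an effect size with an interval, which the plan does not now provide.

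**Conclusion.** The concern holds and is minor. Randomisation is stratified by one versus two expected sessions; the TTP and survival comparison, as written, is not, and the factor is absent from both sections that govern allocation and analysis.

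For survival the cost of leaving the plan as it is runs from nothing to about 6 power points at the HR that 50 deaths can detect, and about 2 points at most at the protocol's HR of 3. For TTP it could reach 8–13 points, but only with a stratum HR of 3 and an assumed 70–90 events, and less if the CT misjudges the stratum. All of this rests on assumed stratum effects and shares. No false-positive inflation arises, and the primary response estimates are not affected.

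**What to change.** - **Section 15.2:** state that permuted blocks are used within two strata, namely first treatment expected on the baseline CT to need one or two embolization sessions.
- **Section 14.0:** compare TTP and survival with a log-rank test stratified by planned one versus two sessions as assigned at randomisation (not by sessions actually given), and report a Cox hazard ratio with 95% CI stratified by the same factor.

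The cost is one sentence in each section. No extra patients, events or procedures are needed, and no new data, since the stratum has to be known to carry out the stratified randomisation. If the factor proves not to be prognostic, stratifying costs at most 0.8 power points in these simulations.

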## 1.0 PROTOCOL SUMMARY AND/OR SCHEMA

Purpose:	The objective of this study is to evaluate hepatic arterial embolization for hepatocellular cancer using microscopic beads and the same microscopic beads loaded with doxorubicin.
Study design:	Single center, single blind, prospective, randomized phase II controlled, to be conducted without crossover with patients recruited over a 2 year period
Study agents:	Biocompatibles LC Bead ( Beads + doxorubicin ), 100-300 microns, 150 mg doxorubicin per procedure with additional 100-300 micron and larger size beads (Bead Block) as necessary to achieve stasis  Bead Block ( Beads ) microsphere, 100-300 micron with additional larger size beads as necessary to achieve stasis
Limitations of Study	LC Bead and Bead Block are both tinted blue. Because doxorubicin is red, the addition of doxorubicin to the embolization microspheres will change the color of the spheres to some degree, and thus it may be possible for the interventional radiologist performing the embolization to differentiate between the two embolics. All other participants performing image and data analysis will be blinded.
Enrollment:	100 patients will be enrolled, 50 in each study arm
Clinical site:	Memorial Sloan-Kettering Cancer Center, NY, NY
Primary endpoint:	Response to treatment by RECIST criteria
Secondary endpoints:	

• Tumor necrosis

• Toxicity

• Time to progression

• Survival

Safety endpoint:	The safety endpoint will be treatment related Serious Adverse Event (SAE) rate, defined by SAE occurring within 30 days of a procedure. SAE is defined as a grade 3 or 4 adverse event using the Common Terminology Criteria for Adverse Events (CTCAE) 3.0.
Primary analysis:	Intent-to-treat analysis
Secondary Analysis:	Per protocol analysis and treated population analysis
Principle Investigator:	[name]

Member  
Department of Radiology  
Memorial Sloan-Kettering Cancer Center  
[name]  
[name]

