### **6.1 Subject Inclusion Criteria**

1. Patient with a confirmed diagnosis of HCC according to EASL criteria for diagnosis, see Appendix 2 who is not surgical resection candidate, or refuses surgery.
2. Patient must be 18 years of age or older.
3. Patient must be Okuda stage I or II, see Appendix 3.
4. Patient must have an ECOG performance status of 0 or 1, see Appendix 1.
5. No prior chemotherapy or biotherapy within 4 weeks of scheduled embolization, with all toxicities, if any, resolved to grade  $\leq$  1
6. Patient must have the following laboratory values confirmed within 4 weeks of registration:
  - a. Creatinine  $\leq$  2.0 the institution ULN
  - b. Platelets  $\geq$  50,000/mm^3
  - c. INR  $\leq$  2.0 for patients who are not on Coumadin
  - d. aPTT  $\leq$  twice control
  - e. Bilirubin  $<$  3 mg/dl
  - f. WBC  $>$  3000 cells/mm^3
  - g. ANC  $>$  1500 cells/mm^3
  - h. Negative serum pregnancy test (Female of childbearing potential only)

A patient will **NOT** be eligible for inclusion in this study if any of the following apply:

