## **12.0 CRITERIA FOR THERAPEUTIC RESPONSE/OUTCOME ASSESSMENT**

All patients will undergo contrast enhanced triple phase CT within 6 weeks of registration and then again within 2-3 weeks of completing their first treatment. Prior to treatment index lesions according to RECIST will be identified and conventional uni-dimensional measurements obtained blinded to the patients treatment group assignment. Response to treatment will be assessed by conventional RECIST criteria (see **Section 4.1**). The electronic data will then be sent to an independent imaging laboratory where an imager not familiar with the same patient's initial data set will create a volumetric profile including volume of tumor and volume of necrosis at time 0. On the initial post-treatment scans the index tumor(s) will once again be identified and measured by an imager blinded to the patient's treatment group, and once again the electronic data will be sent to the imaging laboratory where it will be independently analyzed volumetrically, once again recording tumor volume, and volume of necrosis. These results will be recorded in the electronic database. These linear and volumetric assessments will be repeated each time the patient is imaged for the duration of the study. Any increase in standard manual measurements of >20%, or the development of > 75% increase in enhancing tumor volume will be considered evidence of progression of disease (PD) and so recorded. In addition, patients who develop  $\leq 5\%$  necrosis, by volume, following the initial treatment, or increase of >50% in sum of uni-dimensional measurements following subsequent treatments will be considered treatment failures.

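### TTP and survival are compared by Kaplan-Meier curves and an unadjusted log-rank test only, so no hazard ratio with an interval, crude or adjusted, is planned to inform the next trial

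*Combined protocol and SAP*

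**What the plan says.** Section 14.0 holds the only analysis text for TTP and survival. It plans Kaplan-Meier estimates and then "we will use the log-rank test to compare groups". It claims "approximately 80% power to detect a hazard ratio of 3" with 50 patients per arm, about half of the patients dying, and a 5% type I error rate. It adds that a difference of that size is not expected and that "this aim will primarily serve to obtain preliminary data to plan a future definitive trial".

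The baseline values come from elsewhere in the protocol:

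- **Stage.** Section 6.1 requires "Patient must be Okuda stage I or II". Appendix 3 builds the stage from tumor size, ascites, albumin and bilirubin.
- **AFP, albumin and bilirubin.** Section 8.0 takes these within four weeks of the first embolization.
- **Tumor volume.** Section 12.0 has the imaging laboratory produce a "volumetric profile including volume of tumor and volume of necrosis at time 0", from the scan done before treatment.

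Sections 8.0 and 9.0 say that randomization is stratified by whether one or two embolizations are expected to complete the first treatment. Sections 14.0 and 15.2 mention only permuted blocks, and the log-rank test is not said to use the stratum.

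**The concern.** The planned output does not match the stated purpose. A later trial is sized on an effect estimate and its uncertainty. Section 14.0 even frames its power statement as a hazard ratio, but none is to be estimated. Kaplan-Meier curves give survival by arm, and the log-rank test gives a p-value. Neither is a pre-specified estimate of the treatment effect with an interval.

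In addition, the comparison uses no baseline information. With 50 per arm, the arms can differ by chance in stage, liver function or AFP. If those factors matter for outcome, the difference carries into the observed contrast. Choosing covariates after the results are known would weaken any adjusted figure offered for planning, so they need to be fixed in advance.

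**Working it through.** **1. The plan's own figure.** Section 1.0 states "100 patients will be enrolled, 50 in each study arm". About half dying gives about 50 deaths. With equal arms, SE(log HR) = 2/√50 = 0.283.

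- Schoenfeld power at HR 3, two-sided 5%: Φ(ln 3/0.283 − 1.96) = Φ(1.92) = 97%.
- Freedman: Φ(√50 × (3−1)/(3+1) − 1.96) = Φ(1.58) = 94%.

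The stated 80% is therefore not reproduced. With 50 deaths, 80% power corresponds to HR = exp[(1.96 + 0.84) × 0.283] ≈ 2.21. That is a separate matter and does not affect this point. The plan gives no event number for TTP, so the figures below are for survival.

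**2. What an interval would show.** With 50 deaths the 95% interval is the estimate divided and multiplied by exp(1.96 × 0.283) = 1.74. An estimate of 0.50 would carry an interval of 0.50/1.74 = 0.29 to 0.50 × 1.74 = 0.87. The planned outputs do not report this.

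**3. Chance imbalance.** Let X and Y be the Okuda II counts in the two arms, each Binomial(50, p). The documents give no p, so 40% is assumed, with 30% and 50% as a range. The SD of the difference at 40% is √(2 × 0.4 × 0.6/50) = 9.8 points. Exact probabilities under simple randomization:

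| Assumed share of Okuda II | 10 points or more (\|X−Y\| ≥ 5) | 16 points or more (\|X−Y\| ≥ 8) |
|---|---|---|
| 30% | 33% | 10% |
| 40% | 36% | 13% |
| 50% | 37% | 13% |

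**4. Effect on the crude hazard ratio.** An imbalance d in a factor with prognostic hazard ratio h shifts the crude HR by roughly exp(d × ln h).

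- h = 2, d = 0.10: exp(0.10 × 0.693) = 1.07.
- h = 3, d = 0.10: exp(0.10 × 1.099) = 1.12; simulation with no treatment effect gave 1.11.

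A shift of about 7% to 11% per 10 points is small beside the factor of 1.74 in step 2.

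**5. Power at a true HR of 0.5, log-rank versus adjusted Cox.** All prognostic effects are assumptions. The three-factor sets are hazard ratios for Okuda II, per SD of tumor volume and per SD of log AFP, with 2 to 4 years of follow-up. The single-factor rows use a binary factor with 50% prevalence and 50 events. Several values in a row are separate simulations, some at different event rates.

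| Assumed prognostic effects | Log-rank | Adjusted |
|---|---|---|
| Strong (2, 1.5, 1.4) | 44%, 53%, 54%, 57% | 50%, 63%, 61%, 65% |
| Weaker (1.5, 1.2, 1.2, or similar) | 57%, 60.0% | 59%, 60.8% |
| None, three covariates | 58%, 59.8% | 58%, 58.6% |
| One factor, HR 3 | 62.8% | 66.5% |
| One factor, HR 2 | 68.5% | 67.6% |
| One factor, HR 1 | 69.8% | 66.3% |

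In the single-factor runs, the mean crude HR was 0.507 (prognostic HR 2) and 0.533 (prognostic HR 3), against 0.493 and 0.497 adjusted. With no treatment effect, both analyses rejected in roughly 4% to 6% of trials.

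**6. Can the model be supported?** Arm plus three covariates is four terms: 50/4 = 12.5 deaths per term. The stratum is handled by stratification and uses no coefficient.

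**The case against.** The unadjusted log-rank test is a proper test in a randomized trial, and Section 14.0 says the study emphasizes estimating response rates over testing a hypothesis. Survival is a secondary aim that the plan itself calls preliminary. Kaplan-Meier estimates are useful planning inputs, and a crude hazard ratio needs no covariates. All of this stands, and it limits the point to a missing estimate and a modest refinement.

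Three stronger readings are tempting, and the documents do not support them.

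- **A reader might infer that the planned comparison is invalid or biased.** It is not: type I error stays near 5%. The crude HR lies slightly nearer to 1 largely because it averages over patients with different risks, which makes it a different quantity and not an error.
- **A reader might infer that nothing prognostic is balanced.** Stratifying by one versus two embolizations reflects tumor extent on CT, so tumor size is partly balanced. Eligibility also narrows the range: ECOG 0 or 1, no Child's C, no more than 75% liver replacement, and bilirubin below 3 mg/dl, so Okuda's bilirubin item is not met at entry. Stage, AFP and albumin remain unbalanced by design.
- **A reader might infer a sure gain in power.** No document gives prognostic effects for these values, and the gain disappears when they are weak.

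**Conclusion.** The point holds as a gap in estimation. The plan names no hazard ratio with an interval for TTP or survival, although the stated use of these results calls for one. This part rests on the text alone.

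The case for adjustment is secondary and depends on assumptions. If the factors are strongly prognostic, it adds about 6 to 10 points of power at a true HR of 0.5 and removes noise of about 7% to 11% in the crude HR per 10 points of imbalance. If they are not prognostic, it adds nothing and may cost a little precision. The imbalance frequencies assume an Okuda II share of 30% to 50% and simple randomization. Severity is low to moderate: the aim is secondary and the planned test is sound.

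**What to change.** In Section 14.0, keep the log-rank test as the planned test and add, for both TTP and survival:

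- the unadjusted hazard ratio between arms with its 95% confidence interval, from a Cox model;
- an adjusted hazard ratio with its 95% confidence interval, from a Cox model stratified by one versus two embolizations, with Okuda stage (I or II), log AFP and one baseline tumor size measure as covariates fixed in advance.

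The size measure should come from the pre-treatment CT, because Section 10.0 uses Time 0 for the day treatment is completed. Log volume is suitable if the volumetric method is final. Section 12.0 describes segmentation still under development, so the baseline RECIST sum is the fallback. The choice should be made before outcomes are seen. The text should also say how proportional hazards will be checked.

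The cost is a short paragraph and a few lines of code, with no new data and no change in sample size. The downsides are a slight loss of precision if the covariates are not prognostic, some overlap between Okuda stage and tumor size, and reliance on proportional hazards. Reporting both hazard ratios beside the log-rank test lets readers see whether these matter.

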### **Preliminary Data**

For the past 14 years the protocol used for hepatic arterial embolization at MSKCC employs only an embolic particle targeted to cause terminal vessel blockade and, as a result, ischemic tumor cell death. Knowing that occlusion of the more proximal hepatic vessels results in the development of intrahepatic collateral flow and continued perfusion of the more distal vascular bed, the smallest particles available are used to cause blockade of the terminal hepatic vasculature in an effort to enhance ischemia. Initially, polyvinyl alcohol (PVA) particles were in widespread use and the smallest particles available were 100  $\mu$ , later 50  $\mu$  particles became available. We published our early results using these particles to treat 46 patients in 1998 [Brown KT, 1998]; obtaining results that were not substantially different than those reported contemporaneously by others using various methods of chemoembolization. Since then we have begun using spherical embolic particles, hydrophilic, nonresorbable microspheres produced from an acrylic polymer. Using these particles, and treating over 300 patients with similar characteristics to those reported on by Lo [Lo CM, 2002] and Llovet [Llovet JM, 2002] we have achieved 1, 2, and 3 year survival of 85%, 68%, and 42% [Maluccio 2006]. These results are better than those reported by Lo (56%, 31%, and 26% at 1, 2, and 3 years), and similar to the 82% 1 year and 63% 2 year survival reported by Llovet, but in a much larger group of patients.

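### Section 14.0: the survival power (about 80% at HR 3) and the necrosis precision (±14% of the SD) do not agree with the section's own inputs

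*Combined protocol and SAP*

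**What the plan says.** The trial randomizes two equal arms; Section 1.0 states that "100 patients will be enrolled, 50 in each study arm". Section 14.0 justifies this number by precision, not power, and defines the measure as "precision (half length of the asymptotic confidence interval) of these estimates". It then gives three planning figures.

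- Primary endpoint: "With 50 patients in each arm response rates can be estimated to within +/- 14" percent.
- Necrosis (secondary): "percent necrosis can be estimated to within +/- 14% of its standard deviation". No confidence level is named.
- Survival (secondary, log-rank test): "we will have approximately 80% power to detect a hazard ratio of 3, assuming a median follow-up of 3 years". The follow-up assumption is glossed as "i.e., about half of the patients expiring) and controlling the Type I error rate at 5" percent. Sidedness is not stated. HR 3 is translated into a three-fold median or "improving two-year survival by approximately 20" percent.

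The section adds that a survival difference this large is not expected and that the aim mainly serves to plan a later trial. The only institutional survival figures are in Section 3.0, Preliminary Data: "we have achieved 1, 2, and 3 year survival of 85%, 68%, and 42" percent.

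**The concern.** The survival sentence contains everything needed to check it: patients per arm, hazard ratio, share of deaths, error rate and test. Log-rank power depends almost entirely on the number of deaths, and 50 deaths is a lot for a hazard ratio as large as 3. A claim of only 80% power looked too low.

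The necrosis sentence raised the opposite suspicion. It repeats the wording and the number of the response-rate sentence, but one figure is in percentage points for a proportion and the other is in SD units for a mean. With 50 patients the two should not come out at the same 14% on the same confidence scale.

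At stake is what readers take from the secondary results. If HR 3 is read as the smallest effect the trial can reliably detect, a null log-rank result will be seen as less informative than it is. If ±14% of the SD is read as a 95% margin, the necrosis estimates will be expected to be twice as precise as they will be. Section 14.0 intends the survival data to inform a definitive trial, so these figures may be carried forward.

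**Working it through.** **Inputs.** 50 per arm, 100 in total (Sections 1.0 and 14.0); HR 3, 5% type I error, log-rank test, 3-year median follow-up, about half of patients dead (Section 14.0); survival of 85%, 68% and 42% at 1, 2 and 3 years (Section 3.0). Assumption: two-sided 5%, with one-sided tried as well.

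**1. Survival power**

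Formulas for *d* deaths with 1:1 allocation:

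- Schoenfeld: power = Φ(√d · ln(HR)/2 − 1.960)
- Freedman: power = Φ(√d · (HR − 1)/(HR + 1) − 1.960)

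With d = 50 and HR = 3:

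- Schoenfeld: 7.071 × 1.0986/2 − 1.960 = 1.924, power 97.3%
- Freedman: 7.071 × 0.5 − 1.960 = 1.576, power 94.2%
- Simulated log-rank (20,000 runs, exponential survival): about 97%

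The stated 80% is not reproduced. Deaths needed for 80% power at HR 3:

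- Schoenfeld: 4 × (1.960 + 0.842)² / (ln 3)² = 26.0, so 27
- Freedman: (4/2)² × (1.960 + 0.842)² = 31.4, so 32

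| Deaths | Power at HR 3 (Freedman to Schoenfeld) | HR detectable with 80% power (Schoenfeld to Freedman) |
|---|---|---|
| 50 | 94.2% to 97.3% | 2.21 to 2.31 |
| 42 | 90.0% to 94.5% | 2.37 to 2.52 |
| 30 | 78.2% to 85.3% | 2.78 to 3.09 |

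Other readings of the inputs:

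- One-sided 5%, 50 deaths: 97.1% to 98.7%, further from 80%.
- 45 to 55 deaths: about 92% to 98%.
- Half of the control arm only dead at 3 years: 50 × 0.5 + 50 × (1 − 0.5^(1/3)) = 35.3 deaths, power 84.4% to 90.4%.
- The centre's survival as control, with HR 3: the two-year gain is 0.68^(1/3) − 0.68 = 0.199, which matches the plan's 20 points. Deaths at 3 years are 50 × (1 − 0.42) + 50 × (1 − 0.42^(1/3)) = 29.0 + 12.6 = 41.6, about 42, so power is about 90% to 94.5%. Simulation gives 92.7% with 3-year follow-up for all, and 92.1% with follow-up spread over 2 to 4 years (an assumption).
- 25 deaths, half of one arm's size: 78.4% by Schoenfeld and 70.5% by Freedman.

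**2. Necrosis precision**

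The response-rate figure reproduces as a 95% half-length at a rate of 50%: 1.96 × √(0.25/50) = 0.139. As one standard error it would be √(0.25/50) = 0.071.

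For a mean in SD units with n = 50:

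- one standard error: 1/√50 = 0.141
- 90% half-length: 1.645/√50 = 0.233
- 95% half-length: 1.96/√50 = 0.277 (0.284 with the t distribution)

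The stated 0.14 therefore matches one standard error. An interval of ±0.14 SD has about 68% coverage. A 95% half-length of 0.14 SD would need (1.96/0.14)² = 196 patients per arm.

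**The case against.** On survival, one simple model nearly recovers the stated power. Take 68% two-year control survival and a constant hazard, which the three-fold median translation also suggests. Control survival at 3 years is then 0.68^1.5 = 56%, and with HR 3 the other arm is at 82%. That gives 30.7 deaths, Freedman power of 79.2%, and the stated 20-point gain. The likeliest slip may thus be the remark about half the patients dying, not the power and HR pair. This deserves weight as an explanation, but it does not make the text right: about 31 deaths in 100 is not half, Schoenfeld gives 86.1% and simulation 83.7% for the same scenario, and the 56% conflicts with the 42% three-year survival in Section 3.0.

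On necrosis, no confidence level is stated, the definition of precision is written about the response rates, and 14% of the SD is exactly right as a standard error. So the fault can fairly be described as an unlabelled change of scale. That is accurate, but a reader who meets the same wording and number twice within one section will take them to mean the same thing. If an SD of 50 percentage points had been assumed, the 95% half-length would be ±13.9 points, but the sentence refers to a percentage of the SD.

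On importance, the aims are secondary, the study is not designed to test a hypothesis, and nothing is decided on HR 3. All of this stands and limits the point.

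**Conclusion.** The point holds for both figures.

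- **Survival.** On the stated inputs, power at HR 3 is 94% to 97%, not about 80%, and the HR detectable with 80% power is 2.2 to 2.3, not 3. This rests on reading half of the patients as about 50 of 100 and on a two-sided test; a one-sided test widens the gap. Which input is wrong cannot be settled from the documents. The error is conservative if half the patients do die.
- **Necrosis.** ±14% of the SD is one standard error. On the 95% scale used for the primary endpoint it is ±28%, so the precision appears twice as good as it is. This rests on taking the response-rate figure as the scale the reader will assume.

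The primary ±14%, the sample size and the 20-point two-year gain are consistent with their inputs. This should be corrected, but its effect on the trial is small.

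**What to change.** Leave the sample size unchanged and restate two sentences in Section 14.0.

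1. **Survival.** State the assumed control survival at 2 and 3 years, the expected number of deaths, the sidedness and the formula, and make the power and detectable HR follow from them. At two-sided 5% and 80% power the consistent choices are:
   - about 50 deaths: HR about 2.2 to 2.3
   - about 42 deaths (control survival of 68% and 42%, HR 3): HR about 2.4 to 2.5
   - about 30 deaths: HR about 2.8 to 3.1

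   If 80% power at HR 3 is what was meant, replace the remark about half the patients dying with about 27 to 32 deaths.
2. **Necrosis.** Say that mean percent necrosis in each arm will be known to ±28% of its SD with 95% confidence. If the 14% is also kept, label it as the standard error.

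The cost is two sentences, with no change to conduct or analysis. The stated necrosis precision becomes less favourable; the stated survival detectability improves if about half the patients die.
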